## **8. Data Management and Regulations for Data Traceability**

Subject-related documents are archived per Chinese laws, retained for at least 5 years post-study. All subject data, including identifiable information and medical records, are confidential. Participants are informed of data confidentiality procedures before signing consent forms. Research team members must maintain confidentiality unless authorized.

## **9. Subject Coding, Random Number Table, and Procedures for Storing Case Report Forms**

Same as Section 8.

## **10. Adverse Event Recording, Reporting, and Follow-up**

Any serious adverse events are reported immediately to the clinical trial leader, with detailed documentation of timing, handling measures, and outcomes.

## **11. Statistical Analysis Plan**

Statistical analysis was performed based on the per-protocol (PP) principle. Data are presented as mean  $\pm$  SD for normally distributed continuous variables, median ( $P_{25}$ ,  $P_{75}$ ) for non-normally continuous variables, and frequency (percentage) for categorical variables. The Shapiro-Wilk test was employed to assess the normality of the continuous variables. For normally distributed variables, between-group differences were assessed using unpaired t-test. Repeated measures analysis of variance (ANOVA) and simple effects analysis were conducted to examine changes in visual perceptual function and psychological status before and after VPL training. For each participant, the magnitude of improvement for each visual perceptual function ( $\Delta$ GA,  $\Delta$ 1stM,  $\Delta$ 2ndS,  $\Delta$ 2ndM) was calculated using the formula:  $\Delta I = 20 \log_{10} (Post-training Measure / Pre-training Measure)$  dB. Spearman correlation analysis was performed to evaluate the relationships among general demographic characteristics, visual perceptual function, retinal structure and blood flow parameters,

and psychological scale scores. Multivariable linear regression models were then constructed with  $\Delta$ GA,  $\Delta$ 1stM,  $\Delta$ 2ndS, and  $\Delta$ 2ndM as dependent variables to identify factors associated with training efficacy.

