## **1.2 Research Objectives**

- 1.2.1** To explore the improvement of visual perceptual function in DR patients through VPL training.
- 1.2.2** To provide guidance for visual function recovery in DR patients with visual impairment.

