## **2. Type of Study Design**

Prospective, randomized controlled clinical study.

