### **3. Inclusion and Exclusion Criteria for Subjects**

#### **3.1 Inclusion Criteria:**

- (1) Pre-treatment diagnosis of moderate-to-severe non-proliferative or proliferative DR, with the affected eye having undergone pan-retinal photocoagulation at least 4 weeks prior or vitreoretinal surgery at least 8 weeks prior, with stable conditions and no macular edema or recurrent retinal hemorrhage.
- (2) Best-corrected ETDRS visual acuity (BCVA)  $\geq 0.1$ .
- (3) Clear refractive media.
- (4) Age  $\leq 65$  years, able to understand and cooperate with examinations and training.

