#### **3.3 Elimination Criteria:**

- (1) Temporary refusal of examination or withdrawal from the study.
- (2) Incomplete examination records.

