### **4. Expected Number of Cases Required**

Sample Size: 24 cases (estimated using G\*Power analysis, increased to 36 to account for potential dropout rates).

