### **5. Experimental Methods**

#### **5.1 Grouping**

Subjects are randomly assigned to the Visual Perceptual Learning Training (VPLT) group or the Control Group (CG) using random number generation.

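### Per-protocol is the only analysis principle in a randomised trial and its population is not defined, so the between-group comparisons are open to selection bias of unknown direction and size

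*Combined protocol and SAP*

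**What the plan says.** Section 2 describes the trial as a "Prospective, randomized controlled clinical study", and section 5.1 says: "Subjects are randomly assigned to the Visual Perceptual Learning Training (VPLT) group or the Control Group (CG) using random number generation". Section 11 then opens with the sentence "Statistical analysis was performed based on the per-protocol (PP) principle". It does not say who belongs to the per-protocol set, and the document contains no as-randomised or full-analysis set, no missing-data method and no sensitivity analysis.

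The nearest thing to a rule is section 3.3, whose two elimination criteria are "Temporary refusal of examination or withdrawal from the study" and "Incomplete examination records". That section sits under the general heading "Inclusion and Exclusion Criteria for Subjects". It gives no timing relative to randomisation, does not say which test or follow-up makes a record incomplete, sets no minimum amount of training, and is not cited in section 11.

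Under section 5.2 the training (VPLT) group trains for 40 minutes a day for 3 months and is followed up at 1 and 3 months. The control group has no training and is followed up at 3 months. Section 7 lets any subject withdraw at any time. Section 4 starts from 24 cases, "increased to 36 to account for potential dropout rates".

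**The concern.** Randomisation protects a comparison between arms only if the people compared are the people randomised. If patients are taken out afterwards for reasons linked to how their vision changed, the remaining groups can differ without any effect of training, or a real difference can be hidden or reversed. With no as-randomised result and no count of exclusions by arm, a reader could not tell which had happened.

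Uneven removal is plausible because the demands on the arms differ: daily training and an additional 1-month follow-up fall on VPLT only. The plan also makes room for substantial loss, and leaves open which patients would count as outside the protocol.

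The concern is confined to the between-group comparisons in section 11. These are the unpaired t-tests, and the repeated-measures analyses of visual perceptual function and psychological status so far as they compare the arms over time.

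**Working it through.** **Plan's own figures.** The 24 cannot be reproduced, because section 4 gives no effect size, SD, alpha, power or test. The allowance can be checked: 36 - 24 = 12, and 12/36 = 33% (equivalently 24/(1 - 1/3) = 36). This takes both figures as totals. No dropout rate and no split by arm are stated.

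**Assumptions for the illustration (none is in the documents).** 1:1 allocation, so 18 per arm; the splits of losses; and the link between removal and outcome.

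**Exact identity.** In one arm, let q be the share removed and d the mean change of retained minus removed patients. The all-randomised mean equals (1 - q) x retained mean + q x removed mean, so retained mean minus all-randomised mean = q x d. Hence

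bias = (q x d in VPLT) - (q x d in control).

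Results, with losses written as VPLT/control:
- 8/4 lost, d = 0.5 SD in both arms: 8/18 x 0.5 - 4/18 x 0.5 = +0.11 SD
- 4/8 lost, same d: 4/18 x 0.5 - 8/18 x 0.5 = -0.11 SD
- 6/6 lost, same d: 6/18 x 0.5 - 6/18 x 0.5 = 0
- 6/6 lost, d = 0.5 in VPLT and 0 in control: 6/18 x 0.5 - 0 = +0.17 SD

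The sign depends on which arm loses more, and on whether removal has the same link to outcome in each arm. Equal numbers lost do not guarantee an unbiased result.

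**Effect on the test.** Simulation of 60,000 trials per scenario with no true effect. Removal follows a latent score correlated r with change, the lowest scores are removed, and the arms are compared by a pooled two-sided t-test at 5%. At r = 0.5:
- 8/4 lost: bias about 0.16 SD, type I error 7-8%
- 6/0 lost: bias about 0.26 SD, type I error about 11%
- 6/6 lost, same r in both arms: no bias, type I error about 6%

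At r of 0.1 and 0.2, type I error was at most 6.3% in the scenarios run.

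**What a model can and cannot repair.** Simulation of 20,000 trials, with an assumed baseline-follow-up correlation of 0.5 and no lost outcome recovered. If loss depends only on baseline (correlation 0.5), 6/0 lost biases the change-score comparison by -0.13 SD of change, and a baseline-adjusted model brings this to 0.00. If loss depends on change itself (r = 0.5 given baseline), the adjusted model is still biased by 0.157 residual SD (8/4) and 0.258 residual SD (6/0). The residual SD is 0.866 of the SD of change, so on the same scale these are 0.157 x 0.866 = 0.14 and 0.258 x 0.866 = 0.22 SD.

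**The case against.** The best case for the plan has four parts.

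First, the aim is exploratory: "To explore the improvement of visual perceptual function in DR patients through VPL training". A per-protocol set is also defensible for regressions that ask which factors go with training efficacy. This stands for the regressions. It does not answer the point for the between-group comparisons, where a reader still needs to know whether a difference comes from training or from exclusions.

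Second, the mechanism simulated is not in the documents. Section 3.3 removes people for refusal, withdrawal or incomplete records, and how closely these track outcome is unknown. That stands: the figures show possible scale only, and a weak link gives little inflation.

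Third, section 6 provides phone and WeChat contact to support compliance, which may limit losses. That may help retention, but it does not define an analysis population.

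Fourth, outcomes after withdrawal may not exist, so an as-randomised analysis may recover little. This also stands, and it limits the benefit of the repair.

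Two stronger readings are tempting. A reader might take section 3.3 as the definition of the per-protocol set. It never mentions per-protocol, and section 11 does not cite it, so the link is inference. A reader might also count an extra clinic visit at 1 month as an added chance of exclusion in VPLT. The documents support only an additional follow-up, since section 6 says follow-up is by telephone.

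**Conclusion.** The point holds as a cheap improvement. Per-protocol is the sole stated principle in a randomised controlled trial, its population is undefined, and nothing in the plan provides an as-randomised result or a way of handling missing values. That much rests on the text alone.

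The size does not. Under the assumed splits and links, the bias ranges from nil to about a quarter of an SD in either direction, with type I error between 5% and about 11% at r = 0.5.

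A reader might infer that the analysis favours training, or that bias has occurred. The documents support neither. They give no losses by arm and no reasons for loss, and they do not say whether section 3.3 acts before or after randomisation. More exclusion from VPLT is plausible given its burden, but it remains an inference.

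**What to change.** - **Section 11:** base the between-group comparisons (the unpaired t-tests, and the repeated-measures comparisons of the arms on visual perceptual function and psychological scales) on all randomised participants with available data, in the assigned arm, whatever training was completed.
- **Section 3.3:** state whether the criteria apply before or after randomisation. Let a missed or incomplete examination remove only that measurement, not the randomised participant.
- **Reporting:** give exclusions and their reasons by arm.
- **Per-protocol:** keep it, with a stated definition, as a supportive analysis and for the exploratory regressions on training efficacy.
- **Optional:** a baseline-adjusted likelihood model or multiple imputation, with a sensitivity analysis to departures from missing at random. The model alone does not remove bias when loss depends on change.

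Section 14 gives August 2024 as the completion date. If data collection has ended, the same re-analysis can be done with the data held.

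The cost is wording in two sections, a re-analysis of several outcomes and one table of exclusions by arm. The 3-month follow-up is already planned for both arms. The estimate may be smaller because VPLT patients who did not train as planned stay in, and bias is removed only as far as outcomes exist.

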#### **5.2 Study Design**

Only the surgical eye is included (for bilateral surgery, the eye with better vision meeting inclusion

criteria is selected). The VPLT group undergoes 40 minutes of daily monocular VPL training for 3 months, with follow-ups at 1 and 3 months. The CG receives no training and is followed up after 3 months.

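### Section 11 specifies no baseline-adjusted comparison of the arms at 3 months and does not say which contrast decides efficacy

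*Combined protocol and SAP*

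**What the plan says.** Section 5.1 describes a randomised two-group trial: "Subjects are randomly assigned to the Visual Perceptual Learning Training (VPLT) group or the Control Group (CG) using random number generation". The allocation ratio is not stated. Section 5.2 gives the arms different visit schedules, the training arm "with follow-ups at 1 and 3 months. The CG receives no training and is followed up after 3 months". The arms therefore have only baseline and 3 months in common.

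Section 11 contains three tools that could bear on efficacy:

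- **A t-test.** For normally distributed variables, "between-group differences were assessed using unpaired t-test". It does not say whether this applies to baseline, 3-month or change values, and no covariate is mentioned.
- **A longitudinal model.** "Repeated measures analysis of variance (ANOVA) and simple effects analysis were conducted to examine changes in visual perceptual function and psychological status", with the question put as pre- versus post-training. No group factor or group-by-time interaction is named.
- **Regressions.** The dB change scores for GA, 1stM, 2ndS and 2ndM enter multivariable linear models "as dependent variables to identify factors associated with training efficacy". Neither arm nor baseline is listed as a covariate.

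Section 4 sets 24 cases, "increased to 36 to account for potential dropout rates". It gives no test, effect size, alpha or power.

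**The concern.** Two things are missing: a named efficacy contrast, and an analysis that uses baseline efficiently.

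With no contrast named, the same data can be read through a 3-month t-test, an interaction or a within-arm simple effect, and these need not agree. A simple effect in the training arm alone does not compare the arms. The outcomes are perceptual tests taken more than once, so a retest gain common to both arms is possible. If within-arm simple effects were taken as the evidence, that gain could pass for a training effect.

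On precision, a 3-month t-test ignores baseline, and a change score subtracts it in full. Which does better depends on a correlation that the documents do not give. With 24 planned cases, the wrong choice can cost a large share of the power.

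**Working it through.** **The plan's own figure.** The 24 in Section 4 cannot be reproduced, because its inputs are absent. It can only be back-solved, assuming 1:1 allocation and two-sided 5%. It fits a two-sample t-test at d = 1.20 with 80% power. It equally fits a two-visit interaction (correlation 0.5) at f = 0.30 with 80%, f = 0.35 with 90% or f = 0.40 with 95%. The sample size therefore does not reveal which contrast was planned.

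**What the interaction amounts to.** With two groups and two shared visits, the group-by-time F equals the square of the change-score t. On one test data set both were 2.4385.

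**Variance of the arm difference.** Let n be the number per arm, SD = 1 at both visits, and ρ the baseline-to-3-month correlation:

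- 3-month values only: 2/n
- change score or interaction: 2(1−ρ) × 2/n
- ANCOVA: about (1−ρ²) × 2/n, with one degree of freedom lost and a small cost for chance baseline imbalance

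Since 2(1−ρ) − (1−ρ²) = (1−ρ)² ≥ 0, the ANCOVA variance factor never exceeds that of the change score. At ρ = 0.5 the factors are 1, 1 and 0.75; at ρ = 0.7 they are 1, 0.60 and 0.51.

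**Simulated power.** Assumptions: a true 3-month difference of d = 0.8 SD, two-sided 5%, 1:1 allocation and bivariate normal data. Each setting has 20,000 trials, with the degree of freedom and chance imbalance included.

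| n per arm | ρ | 3-month t | interaction / change | ANCOVA | ANCOVA minus interaction (points) |
|---|---|---|---|---|---|
| 12 | 0.3 | 46.2% | 35.4% | 48.2% | 12.8 |
| 12 | 0.5 | 46.5% | 45.6% | 55.3% | 9.7 |
| 12 | 0.7 | 46.6% | 67.6% | 72.6% | 5.0 |
| 12 | 0.8 | 46.6% | 84.0% | 85.9% | 1.9 |
| 12 | 0.9 | 47.4% | 98.7% | 98.7% | 0.0 |
| 18 | 0.3 | 64.3% | 49.8% | 66.7% | 16.9 |
| 18 | 0.5 | 64.1% | 64.5% | 75.1% | 10.6 |
| 18 | 0.7 | 64.0% | 84.8% | 89.2% | 4.4 |
| 18 | 0.8 | 64.4% | 95.7% | 96.7% | 1.0 |

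A noncentral-t check at 12 per arm gives 46.6% for the 3-month t-test. At ρ = 0.5 and 0.7 it gives 46.6% and 67.7% for change, and 55.8% and 72.4% for ANCOVA. Mean 95% CI width at 12 per arm (3-month / change / ANCOVA) is 1.68/1.68/1.49 SD at ρ = 0.5 and 1.67/1.29/1.23 SD at ρ = 0.7. Type I error is 4.8–5.3% throughout, so each test is valid taken alone.

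**Cost of leaving the contrast open.** In a null simulation at 12 per arm (40,000 trials), accepting either the 3-month t-test or the interaction rejects in about 9–10% of trials per outcome.

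**Within-arm reading.** Suppose there is no training effect, both arms have the same assumed retest gain, and efficacy is read as training arm significant, control arm not. With p the chance that one arm is significant, the rate is close to p(1−p), so it peaks near 25%. For gains of 0.2, 0.3 and 0.5 SD of change, the simulated rates are 8.3%, 12.7% and 22.8% at 12 per arm, and 10.7%, 17.4% and 25.1% at 18. The between-arm change test stays at 4.8–5.1% in the same settings.

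**The case against.** The strongest reply is that simple effects ordinarily follow a factorial model. In a randomised two-arm trial, group-by-time is then the natural reading; it is a valid between-arm test and accounts for baseline by differencing, as does the dB score. On that reading, ANCOVA is only an efficiency preference among valid methods. This is fair as far as validity goes: no bias is alleged, and every test holds its 5% level. It does not supply the missing statement of which test decides, and differencing is not covariate adjustment.

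It can also be said that the size of the gain rests on assumed d, ρ, equal SDs and 1:1 allocation. That stands. The gain over the interaction runs from about 17 points to none, and 18 per arm presumes no dropout. ANCOVA is also not best everywhere. At 12 per arm and d = 0.8, it trails the 3-month t-test slightly at ρ = 0 (45.0% against 46.8%) and at ρ = 0.1 (45.1% against 46.4%). That loss of 1–2 points is small beside what the less suitable named test gives up at higher correlations.

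The within-arm error rates are conditional. The plan nowhere says efficacy will be judged that way, so they show what naming the contrast would prevent, not what will happen.

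Finally, the absence of a primary outcome or multiplicity rule is a real gap, but a separate one that this change does not settle.

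**Conclusion.** The concern holds and should be fixed. It is certain from the text that Section 11 gives neither a baseline-adjusted arm comparison nor a named deciding contrast. The size of the precision loss is uncertain. Under the stated assumptions, at 12 per arm and correlations of 0.3 to 0.8, whichever named test is less powerful trails ANCOVA by about 10 to 39 points: the interaction at 0.3 and 0.5 (12.8 and 9.7), and the 3-month t-test at 0.7 and 0.8 (72.6 − 46.6 = 26.0 and 85.9 − 46.6 = 39.3). If the interaction is what was meant and the correlation is 0.8 or more, the loss is 2 points or fewer, and the remaining defect is one of specification.

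**What to change.** In Section 11, state that for each outcome the efficacy analysis is an ANCOVA of the 3-month value on arm plus the baseline value of that outcome, and that the arm coefficient with its 95% CI is the efficacy contrast.

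- **GA, 1stM, 2ndS and 2ndM:** analyse as 20·log10 of the measure, so the estimate is a between-arm difference in dB. This keeps the plan's own score: because ΔI is the 3-month value minus baseline on that scale, regressing ΔI on arm plus 20·log10(baseline) gives the same arm coefficient.
- **HADs and LVQOL:** keep on their own scales.
- **Simple effects and the 1-month values:** report as descriptive. The 1-month visit exists only in the training arm and cannot enter a between-arm contrast.
- **Regressions on ΔI:** where they are used to explore factors, keep them separate from the efficacy model.

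The cost is SAP wording and one degree of freedom per model, using baseline and 3-month data already planned. Section 11 is written in the past tense and Section 14 gives completion as August 2024. If outcome data by arm have already been seen, the change should be dated and disclosed as made afterwards.

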## **6. Clinical Observation, Follow-up, and Measures to Ensure Subject Compliance**

**Clinical Observation:** Indicators as described in the experimental methods.

**Follow-up:** Conducted via telephone.

**Compliance Measures:** Detailed contact information is collected during hospitalization, with timely follow-up via phone or WeChat post-surgery.

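### The regressions on change scores, as stated, show who changes; they do not show for whom training works, so the training-efficacy label does not follow

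*Combined protocol and SAP*

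**What the plan says.** Section 11 defines a change score in dB: "For each participant, the magnitude of improvement for each visual perceptual function" is 20 log10 of "Post-training Measure / Pre-training Measure". The four scores (GA, 1stM, 2ndS, 2ndM) then become dependent variables in multivariable linear regressions, whose purpose is "to identify factors associated with training efficacy". The section lists no predictors for these models, does not say whether one arm or both enter, and mentions neither an arm term nor an arm-by-factor term. No other section supplies them.

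The design has a randomised comparator. Section 5.1: "Subjects are randomly assigned to the Visual Perceptual Learning Training (VPLT) group or the Control Group (CG) using random number generation". Section 5.2: "The CG receives no training and is followed up after 3 months".

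The last paragraph of section 1.1.3 includes influencing factors in the purpose of the study. The objectives in section 1.2 do not.

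**The concern.** Efficacy of training is a contrast between change with training and change without it. A within-person change score also contains whatever else moves the measure: retest gain, regression to the mean, and recovery after surgery or laser. A factor tied to any of these will correlate with change whether or not the patient trained. If the model cannot tell the two situations apart, such a factor may be reported as bearing on training efficacy although the control arm would show the same relation. Section 1.1.3 says that the study should guide evaluation, follow-up and rehabilitation, so a mislabelled predictor could misinform readers about who benefits.

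**Working it through.** **What each model estimates.** Let x be a factor, b its slope on change without training, d the mean training effect and g the additional slope under training. Expected change is m + b·x in controls and m + d + (b + g)·x in trained patients. Then:

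- trained arm only: slope = b + g;
- both arms with a common slope, 1:1 allocation and equal spread of x: slope = about b + g/2;
- arm-by-factor term in both arms: g.

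Only g concerns the effect of training. If g = 0 and b is not zero, the first two models still show a slope. This needs no numerical assumption.

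**Which model is planned.** The formula speaks of a post-training measure, which leans towards trained patients only. The reference to each participant leaves pooling open. Neither reading yields g without an added term.

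**Illustrative flag rates.** The only design figures are in section 4: 24 cases, increased to 36. That figure cannot be reproduced, because no effect size, SD, alpha, power or dropout rate is given, and this point does not rest on it. Assumed here: 24 and 36 are totals, allocation is 1:1 (12 or 18 per arm), the training effect is 0.8 SD, and one factor has correlation r with change in both arms (g = 0). Two-sided 0.05, 20,000 simulated trials. Entries are the percentage of trials with p < 0.05, for 12 / 18 per arm:

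| r | Trained only | Trained only, two further null predictors | Pooled, no arm term | Pooled with arm term |
|---|---|---|---|---|
| 0.1 | 6.1 / 6.7 | 5.9 / 6.7 | 7.1 / 8.4 | 7.3 / 9.0 |
| 0.2 | 9.7 / 12.5 | 8.4 / 11.3 | 13.9 / 20.0 | 14.8 / 21.9 |
| 0.3 | 16.1 / 23.3 | 12.8 / 20.4 | 26.2 / 38.8 | 29.2 / 42.9 |
| 0.5 | 40.5 / 58.9 | 33.5 / 53.5 | 64.9 / 83.0 | 70.5 / 88.6 |

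At r = 0 the trained-only model gives 5.0 / 4.8. The arm-by-factor test stays between 4.8 and 5.2 at every r.

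Hand check by Fisher's z for r = 0.2, n = 18: atanh(0.2)·√15 = 0.203 × 3.873 = 0.785; P(Z > 1.96 − 0.785) + P(Z < −1.96 − 0.785) = 0.120 + 0.003 = 0.123, against 0.125 simulated.

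**What an interaction could detect.** Since 20 log10(post/pre) = 20 log10(post) − 20 log10(pre), regressing the 3-month dB value or the dB change gives the same interaction estimate once the baseline dB value is in the model. The model has five coefficients (intercept, baseline, arm, factor, arm-by-factor). For a standardised factor and residual SD 1, the SE of the slope difference is about √(2/(n − 3)) with n per arm:

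- n = 12: √(2/9) = 0.471; × t(19 df) 2.093 = ±0.99 (simulated ±0.98);
- n = 18: √(2/15) = 0.365; × t(31 df) 2.040 = ±0.745 (simulated ±0.745).

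For a true slope difference of 0.5, with no slope in controls, simulated interaction power is 18.1% / 27.5%. The trained-only model has 31.8% / 48.0% in the same setting. About 65 per arm would give 79%.

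**Multiplicity.** One to three factors on four outcomes make 4 to 12 tests. If independent, the chance of at least one false positive is 1 − 0.95^4 = 18.5% to 1 − 0.95^12 = 46.0%. If the outcomes correlate 0.5 to 0.8 (assumed), simulation gives 12–16% for 4 tests and 31–42% for 12.

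**The case against.** The strongest reply is that the wording is only loose. Training efficacy may be shorthand for the improvement score just defined, and an association is a descriptive claim. The plan never speaks of effect modification, subgroups or patient selection. On that reading the regressions do what is intended, and the flag rates above are not error rates, because at r = 0.3 or 0.5 the factor truly is associated with change. This stands in part. The rates count as mislabelling only if the result is read as being about the training effect. But the plan's words invite that reading, as does section 1.1.3, which couples the improvement effect of training with its influencing factors. If description is all that is meant, saying so settles the matter.

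It is also fair to say that the consequence is limited and that an interaction model would seldom find anything in a trial of this size. Both are accepted; they are why the wording change comes first.

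Three stronger inferences are not supported:

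- *An interaction has been ruled out, or the models use trained patients only.* Neither is stated. The term is missing from the text, not excluded by it.
- *False claims are likely.* With an assumed slope of 0.8 residual SD (correlation 0.8/√(1 + 0.64), about 0.62), a purely prognostic factor is flagged in 64–99% of simulated trials across the possible models. Nothing in the documents supports so strong a relation. Entry "with stable conditions and no macular edema or recurrent retinal hemorrhage" (section 3.1) argues for weaker ones.
- *Controls have no 3-month perceptual data because section 6 says follow-up is "Conducted via telephone".* The same section refers clinical observation to the indicators in the experimental methods, and those tests can hardly be done by telephone. Section 11 says "between-group differences were assessed using unpaired t-test" and plans simple effects analysis, which suggests repeat testing of controls. The t-test sentence could, however, refer to baseline only. Repeat testing is likely but should be confirmed.

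**Conclusion.** The point holds as a mismatch between model and conclusion. Without an arm-by-factor term, neither reading of the section 11 regressions identifies factors in training efficacy; they identify factors in change. This follows from the specification and does not depend on any assumed rate.

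Its practical size is modest and cannot be fixed from the documents. Under the assumptions above, a factor with no bearing on the training effect would be flagged in 6–9% of trials at a correlation of 0.1 and in 8–22% at 0.2, depending on the model and numbers per arm. These are illustrations only. A reader might infer that the trial's main result is compromised; it is not, because the comparison of randomised groups does not use these regressions.

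**What to change.** **Main change.** State in section 11 which arms and which predictors enter each regression. Report any result from a model without an arm interaction as *associated with change*, not with training efficacy. This costs wording and a more modest claim. If the models have already been run, as the past tense of section 11 and the August 2024 completion date in section 14 may suggest, this alone is the fix.

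**Exploratory addition, if controls have 3-month perceptual measures.** For one to three factors named in advance, fit in both arms the 3-month value (dB scale) on baseline value, arm, factor and arm-by-factor. Where the factor is the baseline value of the same outcome, enter it once with an arm-by-baseline term; entering it twice leaves five columns of rank four, and the model cannot be fitted. Report the interaction estimates with 95% CIs, state the number of tests, and call the results exploratory.

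**Cost of the addition.** It needs one revised model and no extra patients. It gives up power relative to the trained-only model in exchange for the right contrast, and its intervals will be wide. With 4 to 12 tests, an isolated significant interaction should not be presented as a finding.
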